5.0 STUDY MEDICATION

5.1 Abatacept

ABT is a fully human soluble fusion protein of the extracellular domain of cytotoxic T lymphocyte

antigen 4 (CTLA-4) linked to a modified Fc portion of human IgG1, a physiological antagonist of the T cell co-stimulatory molecule CD28 by binding to CD80/CD86 with higher affinity than CD28. By this action, ABT inhibits T cells as a costimulatory signal is needed for full T cell activation. Activated T lymphocytes are implicated in the pathogenesis of My-ILD (see above). ABT decreases T cell proliferation and inhibits the production of the cytokines TNF alpha (TNF α), interferon- γ , IL-2, IL-6, some of which are also linked to the pathogenesis of myositis.

5.1.1 Abatacept Dosage and Administration

A self-administered weekly dose of 125 mg SQ will be used in this 24-week trial and open label phase of 24 weeks. Abatacept is supplied in prefilled syringes or ClickJectTM prefilled autoinjectors for Subcutaneous (SC) injections. The clinical site will provide instructions to the subject how to safely administering the study medication subcutaneously at the Visit 1 time-point.

5.1.2 Abatacept Storage

Abatacept subcutaneous syringes or autoinjectors should be stored under refrigeration (2-8°C) and protected from light. Do not allow the pre-filled syringe or autoinjector to freeze and do not use beyond the expiration date on the syringe or autoinjector. If frozen, do not use.

Access must be restricted to authorized personnel. The intake of all study drugs will be recorded in the Case Report Form (CRF). The medication provided for this study is for use only as directed in the protocol. Clinical center pharmacies will be responsible for the storage, handling, and dispensing of study drug. The Coordinating Center will monitor all documentation related to drug handling activities to ensure adherence to proper procedures.

All used and unused study drugs must be retained at the clinic for reconciliation and accountability and should be destroyed at the study site by authorized personnel according to approved procedures or collected by the monitor for disposal.

Study drugs are to be prescribed only by a physician named in the Form FDA-1572. Under no circumstances will the investigator allow the study drug to be used other than as directed by the protocol.

5.1.3 Study Drug Labeling

Bristol Myers Squibb will provide study drug and placebo. The kits and pre-filled syringes will contain the same labeling to ensure blinding of the subject. Study drug should dispensed at the clinical site by the unblinded investigational pharmacist. Study medication will be labeled with the following information:

- Subject ID
- Study protocol number
- Investigational new drug statement
- Storage conditions and expiration date

5.1.3 Abatacept Overdosage

Doses up to 50 mg/kg have been administered intravenously without apparent toxic effect. In case of overdosage, it is recommended that the patient be monitored for any signs or symptoms of adverse reactions and appropriate symptomatic treatment instituted.

5.2 Other Study Drug(s)

Placebo will be prepared as described above in 5.1.3.

6.0 RISK AND BENEFITS

6.1 Study Medication Risks

A cumulative review of serious and non-serious ADRs was performed from completed double blind, placebo-controlled studies for the RA indication (7 IV and 2 SC studies) and also from ongoing studies where the unblinded data are available, which included studies in psoriatic arthritis (PsA). Assessment of ADRs from one ongoing study in PsA was also performed. The ADRs in patients with PsA are similar to those reported in patients with RA in terms of type, severity, and nature of ADRs. As of 30-Jun-2016, the following serious and non-serious ADRs have been reported in clinical studies with abatacept treatment.

Serious and non-serious infections with common pathogens such as bacterial, viral, and fungal are considered expected in patients treated with abatacept, since abatacept modulates the immune system. The list is presented by SOC and frequency using the following categories: very common ($\geq 10\%$); common ($\geq 1\%$ to $< 10\%$); uncommon ($\geq 0.1\%$ to $< 1\%$); rare ($\geq 0.01\%$ to $< 0.1\%$), or very rare ($< 0.01\%$).

The following is an integrated summary of the Adverse Drug Reactions in Subjects Treated with Abatacept in Clinical Studies

Common Adverse Events ($\geq 1\%$ to $< 10\%$):

Administration Site Reactions: Generalized fatigue and injection site reactions

Gastrointestinal Disorders: abdominal pain, diarrhea, dyspepsia, mouth ulceration and nausea

General Disorders and Infestations: asthenia, bronchitis, urinary tract infection, upper respiratory tract infection, herpes simplex, ear infections and oral herpes

Nervous System Disorders: dizziness and headache

Respiratory, Thoracic and Mediastinal Disorders: cough

Uncommon Adverse Events ($\geq 0.1\%$ to $< 1\%$)

Administration Site Conditions: influenza-like illness

Blood and Lymphatic System Disorders: leukopenia and thrombocytopenia

Cardiac Disorders: bradycardia, palpitations and tachycardia

Ear and Labyrinth Disorders: vertigo

Eye Disorders: conjunctivitis and reduced visual acuity

Gastrointestinal Disorders: gastritis and aphthous stomatitis

Immune System Disorders: urticaria

Infections and Infestations: pneumonia, herpes zoster, cellulitis, lower respiratory tract infections, tuberculosis, nasopharyngitis, sinusitis, tracheitis, rhinitis, infected skin ulcer, onychomycosis, tooth infection and pyelonephritis

Investigations: increased weight, Transaminases increased

Nervous system disorders: paraesthesia

Malignancies: basal cell carcinoma

Psychiatric Disorders: anxiety, depression and insomnia

Reproductive System and Breast Disorders: amenorrhea, menorrhagia

Respiratory, Thoracic and Mediastinal Disorders: wheezing, chronic obstructive pulmonary disease and dyspnea

Skin and Subcutaneous Tissue Disorders: alopecia, dermatitis, dry skin, hyperhidrosis, increased tendency to bruise, pruritis, erythema and acne

Vascular Disorders: flushing, hot flush and hypotension

Immune System Disorders: drug hypersensitivity

Musculoskeletal and Connective Tissue Disorders: pain in extremity, arthralgia

Very Rare Adverse Events (< 0.01%)

Infections and Infestations: sepsis and diverticulitis

Psychiatris Disorders: sleep disorders

Investigations: abnormal liver function test

Malignancies: lymphoma

Antirheumatic therapies have been associated with hepatitis B reactivation.

Adult COPD patients treated with abatacept in RA developed adverse events more frequently than those treated with placebo, including COPD exacerbations, cough, rhonchi, and dyspnea. Use of abatacept in patients with COPD should be undertaken with caution and such patients should be monitored for worsening of their respiratory status.

6.2 Other Risks

Physical Activity Monitor (PAM) Use: There is the possibility of minor skin irritation associated with wearing the PAM device. There may be minor risk of skin irritation from use of the elastic belt if used with the PAM device. Keeping the band clean, dry and loosely fitting will help reduce this risk.

Blood Drawing: Subjects may experience pain, bruising and/or bleeding at the site of the needle insertion for blood drawing. Very rarely an infection may occur at the site. Subjects may also experience dizziness and/or fainting.

Risk of Breach of Confidentiality: Study data and blood specimens collected during the course of this trial will be labeled with a study code and contain no personal subject identifiers that could directly identify the subject and will be stored in a secure location; however there is a chance that a breach of confidentiality will occur and the subject personal or medical health information may be inappropriately distributed.

Data that is transferred from your FitBit One ® device will not contain any identifiable personal information. The data will be stored on a secure network server located in the Department of Medicine, Division of Rheumatology. Study data will be stored in the Rheumatic Disease Management System (RDMS) located at the University of Pittsburgh, Division of Rheumatology which is located on a secure server behind a network firewall. There is the possibility that if the results of the research studies involving biologic samples or genetic material were to become known this information could affect the subjects ability to be insured or employed, reputation, and future plans for children, or family relationships. Although every reasonable effort has been taken,

confidentiality during Internet communication activities cannot be guaranteed and it is possible that additional information beyond that collected for research purposes may be captured and used by others not associated with this study.

Reproductive Risks: The effect of the study drug on the unborn child is unknown.

Consequences of additional therapy restrictions: There is a risk for deterioration in the subjects' condition. New symptoms occurring during the treatment period requiring an unscheduled physician visit, emergency department evaluation, hospitalization or change in immunosuppressive therapy will be evaluated by the principal investigator. Determination will then be made by the principal investigator if additional medication is necessary.

Genetic Samples: It would be rare (less than 1% of cases or in less than 1 out of 100 cases) that if the results of the research studies involving genetic material were to become generally known the information could affect the subjects ability to be insured, ability to be employed, r future plans for children, or family relationships.

7.0 OBSERVATIONS PER VISIT

7.1 Screening Visit (Visit 0)

The following assessments will be performed during the Screening Visit:

Screening Visit (Visit 0)

1. Obtain informed consent from the subject.
2. Review concomitant medications for defined study washout and restriction of immunosuppressive (IS) medications.
3. Urine Pregnancy (if applicable) for all females of childbearing potential.
4. Obtain safety screening tests to include: serologies for Hepatitis B (Hep B surface Ab, surface antigen and core antibody), Hepatitis C (Qualitative HCV antibody) and tuberculosis (Quantiferon TB Gold) if a negative result was not obtained **within the last year**. If Quantiferon gold is non-interpretable or cannot be done, then skin PPD test for tuberculosis should be done.
5. Pulmonary Function Test (PFT) with DLCO should be obtained.
6. If a High-Resolution Computed Tomography (HRCT) chest has been completed as part of the patients' standard of care the results should be recorded on the HRCT chest ILD Assessment Form.
7. Brief Evaluation (history/physical)
8. Obtain and record vital sign measurements.
9. Complete screening evaluation, demographics and screening criteria assessments.

7.2 Other Study Visits

Study Visits 1, 2 and 3 (Weeks 0, 12, and 24)

Subjects who are eligible will visit the study site and enter the randomized treatment phase after randomization. Visit 1 should take place within 21 days after the Screening Visit.

All eligible subjects will receive their first injection of either abatacept 125mg SQ injection or placebo as per randomization at Visit 1. The following assessments will be performed:

The following research procedures will be conducted at Visits 1, 2 and 3 unless otherwise noted:

- Review concomitant medications
- A urine pregnancy (if applicable) will be performed for all females with child bearing potential.
- Site pharmacist will randomize subject to receive either study drug or placebo.
- Perform and record functional test (6 minute walk distance test - 6MWD)
- Administer patient questionnaires to include: dyspnea, patient global, SF-36 and health assessment questionnaires and patient assessment of change
- Site Investigator to perform Manual Muscle Test (MMT-8)
- Site Investigator to complete MDAAT, brief physical exam and physician assessment of change
- Obtain safety screening tests to include: creatine kinase(CK), aldolase, complete blood count with differential, serum creatinine and liver function tests
- Obtain research repository blood per study schema (Appendix A)
- Instruct the subject on how and when to use the FitBit One ® device. Patient will wear FitBit device for 7 consecutive days one a month for 6 months. Refer to Manual of Operations for specific procedures for syncing the device. - **visit 1 only**
- A pulmonary function test will be performed at **visits 2 and 3 only**
- Assess and record adverse events (if applicable) – **visits 2 and 3 only**
- If a High-Resolution Computed Tomography (HRCT) chest has been completed as part of the patient standard of care, the research coordinator will obtain and record the results of this test for research purposes at **visit 1 and 3 only**. A CD of HRCT chest (at baseline and follow up) should be mailed to coordinating center for centralized evaluation in future.
- **At visit 1 only**, you will instruct the subject on how to do the subcutaneous injection of the study drug. The subject will self-administer the study drug at Visit 1 to ensure adequate knowledge. Study drug will be dispensed to the subject at study **visits 1 and 2** (approximately 11 - 12 pre-filled syringes) to continue weekly at home. Note at study **visit 3**, that open label drug should be dispensed to the subject if continuing into the open label Phase II of the study.

Subjects will be informed that the FitBit device must be returned to the research team once they have completed the trial. The FitBit device will be then be re-assigned to future subjects at your site. The FitBit device is setup with individual accounts therefore no data from a previous participant will remain on the device. Please refer to the Manual of Operations for further guidance on setting up a de-identified account for each participant.

The following research activities will occur in between study visits 1, 2, 3 and 4:

- Approximately one week after the subject has been randomized (Visit 1) at the study center, you should call the subject to determine if the subject has experienced any adverse

- events, difficulty with administering the self-injection and to confirm steroid taper compliance. This call should be documented in your site source documentation.
- To insure that we are capturing and addressing potential side effects or deterioration in condition, the coordinators were instructed to call the subject monthly to review for adverse events, steroid taper compliance, and any signs of deterioration from the steroid taper. The call will be documented in the sites source documentation.

Unscheduled Visits: The subject should be seen for an unscheduled visit if any worsening in condition has occurred.

The following research procedures will be conducted at an unscheduled visit:

- Review concomitant medications
- Administer patient questionnaires to include: dyspnea, patient global, and health assessment questionnaires and patient assessment of change
- Site Investigator to perform Manual Muscle Test (MMT-8)
- Site Investigator to complete MDAAT, brief physical, physician global assessment exam and physician assessment of change
- A pulmonary function test (PFT) will be performed as SOC for worsening condition as deemed necessary by investigator.
- Assess and record adverse events (if applicable)
- High-Resolution Computed Tomography (HRCT) will be performed as SOC for worsening condition as deemed necessary by investigator.
- The research coordinator will obtain and record the results of HRCT or PFT if any of these tests are conducted as standard of care.

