No other concomitant IS agent is allowed (e.g. IVIG, plasmapharesis, rituximab, methotrexate, tacrolimus, cyclosporine, other biologics. Hydroxychloroquine and pirenade **are permitted** during the trial if on a stable dose for 4 weeks prior to trial entry.

Forced steroid taper (Prednisone or other steroid in prednisone equivalent doses) in subject on a stable dose of steroid 2 weeks prior to visit 1.

a. **Steroid Tapering:** May begin within or at 1 week after beginning study drug. Goal is to taper steroid to 5 mg or lower dose within 8 weeks. Recommended daily prednisone taper (or other forms of steroid in equivalent doses)

- i. 60 mg decreased to 40 mg after 1 week
- ii. 40 mg decreased to 30 mg after 1 week
- iii. 30 mg decreased to 20 mg after 1 week
- iv. 20 mg decreased to 15 mg after 1 week
- v. 15 mg decreased to 10 mg after 1 week
- vi. 10 mg decreased to 7.5 mg after 1 week
- vii. 7.5 mg decreased to 5 mg after 1 week
- viii. Further decrease as per treating physician.

b. **Steroid at Entry:** Maximum steroid dose allowed at study entry is ≤ 60 mg/day prednisone (or other forms of steroid in equivalent doses). If on a lower dose then the tapering scheme noted above should be employed based on the entry dose. Patients not on steroids are allowed in the study and are not allowed to start new steroids unless there is a disease flare.

c. **Steroid Dosing During Flare:** If in the clinical site investigator's opinion there are complications or worsening of disease that necessitate an increase in the prednisone dose (or other forms of steroid in equivalent doses) then the smallest reasonable increase should be considered (maximum increase of prednisone equivalent of 20 mg/day is allowed). After the increase, subjects should resume the prednisone taper noted above.

Concomitant medications will remain unchanged throughout Phase I, except changes made per the rescue medication protocol. During the open label Phase II, concomitant medications adjustments are permitted even if the subject has not met the definition of worsening.

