SAEs, whether related or not related to study drug, as well as pregnancies, must be reported to BMS within 24 hours. SAEs must be recorded on the MedWatch form; pregnancies must be reported on a Pregnancy Surveillance Form.

- An SAE report should be completed for any event where doubt exists regarding its seriousness.
- For studies with long-term follow-up periods in which safety data are being reported, include the timing of SAE collection in the protocol.
- If the investigator believes that an SAE is not related to study drug, but is potentially related to the conditions of the study (such as withdrawal of previous therapy or a complication of a study procedure), the relationship should be specified in the narrative section of the SAE Report Form.
- If only limited information is initially available, follow-up reports are required. (Note: Follow-up SAE reports should include the same investigator term(s) initially reported.)

If an ongoing SAE changes in its intensity or relationship to study drug or if new information becomes available, a follow-up SAE report should be sent within 24 hours to BMS (or designee) using the same procedure used for transmitting the initial SAE report. All SAEs should be followed to resolution or stabilization.

Non-serious Adverse Event Collection and Reporting

The collection of non-serious AE information should begin at initiation of study drug. All non-serious adverse events (not only those deemed to be treatment-related) should be collected continuously during the treatment period and for a minimum of 30 days following the last dose of study treatment.

All non-serious AEs must be reported by confirmed fax transmission or reported via electronic mail to:

Non-serious AE Email Address: [contact]

Non-serious AE [contact]

Non-serious AEs should be followed to resolution or stabilization, or reported as SAEs if they become serious. Follow-up is also required for non-serious AEs that cause interruption or discontinuation of the BMS product associated with this study and for those present at the end of the study, as appropriate.

MedWatch 3500A Reporting Guidelines

In addition to completing appropriate patient demographic and suspect medication information, the report should include the following information within the Event Description (section 5) of the MedWatch 3500A form:

- Treatment regimen (dosing frequency, combination therapy)
- Protocol description (and number, if assigned)

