APPENDIX B: STUDY FLOW CHART/SCHEMA

Month	0-21 days before study drug	Open Label												Unscheduled Visit
		0	1	2	3	4	5	6	7	8	9	10	11	12
(weeks)	0	+7 days from V1	8	12	16	20	24	28	32	36	40	44	48	
Visit	Screen	1	Call	Call	2	Call	Call	3	Call	Call	4	Call	Call	5
	or													
	Visit 0													
Safety Laboratory Testing														
Urine Pregnancy (if applicable)	X	X			X			X			X			X
CK, Aldolase		X			X			X			X			X
CBC, Creatinine, LFT		X			X			X			X			X
Serologies (HCV, HBV) or TB screening if not done within last 1 year	X													
Data Collection														
Screening demographics	X													
Screening evaluation	X													
Screening criteria	X													
Randomization form		X												
PFT (FVC, FEV1, DLCO)	X			X			X						X	**
HRCT chest (if done as SOC) *	X							X					X	**
HRCT ILD Assessment Form (if done as SOC)	X							X					X	
Dyspnea questionnaire		X		X			X			X			X	X
Patient Global Assessment		X		X			X			X			X	X
HAQ		X		X			X			X			X	X
MMT-8		X		X			X			X			X	X

MDAAT		X		X		X		X				X	X
Physician Global Assessment		X		X		X		X				X	X
Physician Assessment of Change				X		X		X				X	X
Patient Assessment of Change				X		X		X				X	X
SF 36 QoL Questionnaire		X		X		X		X				X	
Brief Evaluation (history/physical)	X			X		X		X				X	X
Six Minute Walk Distance (6MWD)		X		X		X		X				X	
Average daily step count on Fitbit One ® (measured for 7 days at baseline and every month for 6 months)		X		X		X							
Adverse Event/Tolerability Monitoring		X		X		X		X				X	X
Follow Up Call (assess AE's.confirm steroid taper per protocol and subjective clinical worsening)			X	X		X	X	X	X			X	
Bio-specimen Repository Collection		X		X		X		X				X	
RESEARCH SPECIMEN COLLECTION													
PAXGene tube (ml)		8		8		8		8				8	
Stored cells (ml) Green Top		16		16		16		16				16	
Stored Serum (ml) SST		16		16		16		16				16	

* An HRCT scan done as SOC within the last 6 months is required for entry into the trial to meet eligibility criteria.

** HRCT and PFT done as SOC for worsening condition as deemed necessary by investigator.

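### Appendix B shows no contact from day 7 to week 8 although section 7.2 asks for monthly calls, and no contact is scheduled to complete the 30-day adverse event window of section 11.2

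*Combined protocol and SAP*

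**What the plan says.** **Calls.** Section 7.2 lists two separate items for the time between visits. The first is: "Approximately one week after the subject has been randomized (Visit 1) at the study center, you should call the subject". The second states that "the coordinators were instructed to call the subject monthly to review for adverse events", and also to check taper compliance and deterioration caused by the taper. The list opens with: "The following research activities will occur in between study visits 1, 2, 3 and 4".

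**Flow chart.** In Appendix B the month-1 column is the call 7 days after Visit 1. The next column is the week-8 call, followed by Visit 2 at week 12. Calls and visits then alternate every 4 weeks to Visit 5 at week 48. The calls are meant to assess adverse events and to "confirm steroid taper per protocol and subjective clinical worsening".

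**Taper.** Section 3.1.1 says of the steroid taper: "May begin within or at 1 week after beginning study drug". The recommended steps are weekly, beginning with "60 mg decreased to 40 mg after 1 week", and the stated aim is: "Goal is to taper steroid to 5 mg or lower dose within 8 weeks". Patients entering on a lower dose join the scheme at that dose. Patients not taking steroids are eligible.

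**Collection window.** Section 11.2 requires serious events to be reported until 30 days after dosing stops. Non-serious events are to be collected during treatment and "for a minimum of 30 days following the last dose of study treatment". Section 3.4 places the Phase I closing visit at week 24, and section 7.3 places the open-label visits at weeks 36 and 48. Sections 7.2 and 7.3 and Appendix B set no later contact.

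**The concern.** A site that works from the flow chart would not deliver the monitoring that section 7.2 describes. The missing contact falls in the weeks when steroids are being withdrawn, which is the reason section 7.2 gives for calling. No other scheduled contact fills those weeks: after Visit 1 the next scheduled visit and the next safety laboratory tests are at week 12.

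Timing also matters for one secondary endpoint. Under section 4.5.3, whether added immunosuppression counts as treatment failure depends on whether it came before or after 8 weeks on study drug. A deterioration first heard of at the week-8 call would have to be dated by recall, right at that boundary.

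The second gap concerns completeness. Section 11.2 sets a collection duty that runs past the last scheduled contact, so events in that period reach the database only if the patient or a treating physician volunteers them. Adverse events are the primary safety outcome (sections 3.3.1 and 12.2.1).

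**Working it through.** The point rests on calendar arithmetic; no sample size or power figure is involved.

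**1. The stated taper duration reproduces.** The scheme 60, 40, 30, 20, 15, 10, 7.5, 5 mg has seven weekly steps. The 5 mg dose is reached on day s + 6 × 7, where s is the day of the first step:
- s = 0 gives day 42
- s = 7 gives day 49
- s = 14 gives day 56

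All are within the stated 8 weeks (56 days).

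**2. Contacts in Appendix B.** The month row (0 to 12), the week row (0, day 7, 8, 12, 16, … 48) and the visit row (1, Call, Call, 2, … 5) each hold 13 entries and line up one to one.
- Visit 1 to first call: 7 − 0 = 7 days
- First call to second call: 56 − 7 = 49 days
- Every later interval: 28 days

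Reading monthly as every 4 weeks, as Appendix B does elsewhere, section 7.2 implies a contact at about day 28. Adding it splits the gap into 21 and 28 days, so the longest gap falls from 49 to 28 days.

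**3. Taper steps inside the gap.** With the first step on day 7, steps fall on days 7, 14, 21 and so on. Those strictly between day 7 and day 56 are:

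| Entry dose (mg) | Steps to 5 mg | Last step (day) | Steps in the gap |
|---|---|---|---|
| 60 | 7 | 49 | 6 |
| 40 | 6 | 42 | 5 |
| 30 | 5 | 35 | 4 |
| 20 | 4 | 28 | 3 |
| 15 | 3 | 21 | 2 |
| 10 | 2 | 14 | 1 |
| 7.5 | 1 | 7 | 0 |

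From 60 mg with the first step on day 0, the steps in the gap are days 14 to 42, which is five. With the first step on day 14 they are days 14 to 49, which is six.

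**4. Span of the calls.** Section 7.2 covers Visits 1 to 4, that is to week 36. Appendix B also has calls at weeks 40 and 44, between Visits 4 and 5.

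**5. The 30-day window.** The exact day of the last dose is not stated. Section 7.2 dispenses about 11 to 12 syringes at each of Visits 1 and 2, and section 5.1.1 sets weekly dosing for 24 weeks. Twenty-four weekly doses from week 0 put the last Phase I dose at about week 23, and by the same reasoning the last open-label dose at about week 47. Days without a scheduled contact = (last-dose day + 30) − (day of final contact):

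| Last dose | Window ends | Final contact | Days uncovered |
|---|---|---|---|
| Week 23 (day 161) | day 191 | day 168 | 23 |
| Week 24 (day 168) | day 198 | day 168 | 30 |
| Week 47 (day 329) | day 359 | day 336 | 23 |
| Week 48 (day 336) | day 366 | day 336 | 30 |

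**6. Early stoppers in Phase I.** A patient who stays on the visit schedule has a contact at or after day 30 post-dose if 7L + 30 ≤ 168, where L is the week of the last dose. L = 19 gives 163, which meets this. L = 20 gives 170, which does not. So last doses at weeks 0 to 19 are covered. Those at weeks 20 to 23 are covered only if the patient continues past week 24.

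**The case against.** **The taper is not wholly unmonitored.** A reader might infer that the gap covers the entire forced taper, or its steepest part. The documents do not support that. The taper may start by day 7, so the first and largest reduction (60 to 40 mg) can fall at or before the day-7 call, which checks compliance. The full seven steps apply only at the maximum entry dose, and some patients have no taper at all.

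**Events in the taper are more likely late than lost.** The text of section 7.2 still asks for monthly calls, the week-8 call and Visit 2 collect events, and worsening triggers an unscheduled visit. This stands.

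**The 30-day window is not empty.** A reader might infer that no contact at all falls within it. With weekly dosing, the closing visit probably comes about 7 days after the last dose. What stands is that no contact completes the window.

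**The randomised comparison may be little affected.** Both arms share one call schedule. Section 3.3.3 summarises events during the treatment period, events after week 48 follow an uncontrolled phase, and the sponsor expects everyone to enter that phase. So a distorted treatment comparison does not follow from these gaps.

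**Early leavers are mostly covered.** Section 4.5.3 keeps patients who stop study drug on the visit schedule, and section 4.4 requires an attempt to ask about new events before a patient is classed as lost. That leaves those who leave the study itself. Section 9.1 directs study discontinuation for hypersensitivity, and section 4.4 sets a final evaluation at withdrawal with no later scheduled contact.

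**Appendix B is damaged in extraction.** The visit row has eight calls while the follow-up call row shows seven marks, so the body rows cannot be relied on. The argument uses only the three header rows, which agree. Appendix B could be read as one contact per month with the first placed at day 7; but section 7.2 lists the day-7 call and the monthly calls as separate items.

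**Conclusion.** The concern holds in two limited parts.

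First, section 7.2 and Appendix B give different call schedules. Appendix B leaves 49 days without a contact, against 28 days between all later contacts. The gap holds five or six of seven taper steps for entry at 60 mg and none for entry at 7.5 mg. The two also disagree on calls between Visits 4 and 5. This rests on the header rows being intact and on the day-7 call being additional to the monthly ones.

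Second, nothing is scheduled to complete the 30-day window in section 11.2 for patients leaving at week 24 or week 48. About 23 days are uncovered if the last dose is a week before the closing visit, and 30 if it is on that day. The collection duty exists; only a contact to discharge it is absent.

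The likely consequences are late or poorly recalled events and conflicting site instructions during the taper, and possibly missed events after the last dose. No between-arm bias is shown. This is a minor but worthwhile correction.

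**What to change.** Reconcile section 7.2 and Appendix B so that both give the same contact schedule, with explicit weeks, including the taper period and the interval between Visits 4 and 5. If the monthly calls are meant to be additional to the day-7 call, Appendix B needs a week-4 contact.

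Add to both places one safety call at or after 30 days from the last dose for any patient whose final scheduled contact comes sooner: those leaving at week 24 or week 48, and those withdrawn from the study. With last doses at weeks 23 and 47 the call would fall on or after day 191 or day 359; with last doses on the closing-visit day, on or after day 198 or day 366. Record the date of the last dose so that the window can be verified.

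The cost is a flow-chart correction and one or two calls per patient, or 20 to 40 calls for 20 patients. No dose, taper step or rescue rule changes.
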